## **8.0 CRITERIA FOR REMOVAL FROM PROTOCOL THERAPY AND OFF STUDY CRITERIA**

### **8.1 Criteria for Removal from Protocol Therapy**

- a) Progressive disease.
- b) Unresectability of tumors following 4 cycles of chemotherapy in intermediate-risk patients.
- c) Unresectability of tumors following 10 cycles of chemotherapy in high-risk patients who responded (RECIST CR or PR) to “up-front” window therapy.
- d) Unresectability of tumors following 8 cycles of chemotherapy in high-risk patients who did not respond to “up-front” window therapy.
- e) Inability to have a liver transplant by the specified protocol timepoints for reasons unrelated to hepatoblastoma.
- f) Failure to begin protocol therapy within 42 days of initial biopsy or definitive surgery whichever occurs last.
- g) Failure to resume post resection chemotherapy within 42 days of resection in intermediate- or high-risk patients.
- h) Refusal of further protocol therapy by patient/parent/guardian.
- i) Completion of planned therapy.
- j) Physician determines it is in patient’s best interest.
- k) Development of a second malignant neoplasm.
- l) For high-risk patients, if the investigator selects a post-induction regimen that is not indicated by the central review of response.

Patients who are off protocol therapy are to be followed until they meet the criteria for Off Study (see below). Follow-up data will be required unless consent was withdrawn.

### **8.2 Off Study Criteria**

- a) Death.
- b) Lost to follow-up.
- c) Patient enrollment onto another COG study with tumor therapeutic intent (eg, at recurrence).
- d) Withdrawal of consent for any further data submission.
- e) Tenth anniversary of the date the patient was enrolled on this study.
- f) Definitive surgery does not confirm the diagnosis of hepatoblastoma or reveals another pathological diagnosis in patient who was enrolled emergently without initial biopsy because too sick.

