### 9.2 Statistical Analysis Methods

#### Statistical Considerations

Patients will be enrolled to the study for Five years and followed for an additional year, by which time we expect most disease-related analytic events will have occurred. The design objectives will be different for the four subgroups: (1) Stage I PFH patients (stratum 1) with AFP  $\geq$  100 ng/mL or AFP not obtained prior to surgical resection of tumor; (2) low risk patients (stratum 2) defined as patients with Stage I non-PFH, non-SCU; Stage II non-SCU (3) intermediate risk patients (stratum 3); and (4) Stage IV patients or patients with AFP < 100 ng/mL at diagnosis (stratum 4). EFS will be the time from patient enrollment until last follow-up or an analytic event is observed, whichever comes first. Analytic events are: (1) progression of existing disease or occurrence of disease at new sites; (2) treatment failure defined as the presence of disease after four cycles of chemotherapy and post-induction surgery (if attempted) for patients enrolled with Stage III disease or presence of disease after planned chemotherapy (eight cycles for non-responders, ten cycles for responders) for patients enrolled with Stage IV disease (3) death from any cause prior to disease progression or diagnosis of a second malignant neoplasm; or (4) diagnosis of a second malignant neoplasm. Survival will be the time from enrollment until death from any cause or last follow-up, whichever comes first.

[Section 3](#) requires that planned start of systemic therapy for patients whose protocol prescribed therapy includes chemotherapy must be within 42 days of enrollment. Experience from prior COG studies of hepatoblastoma demonstrates that this can be accomplished in most patients. All patients who die within 42 days of enrollment will be considered in the analytic plans below. All patients who survive more than 42 days after enrollment and whose protocol therapy prescribes chemotherapy but who do not have such systemic therapy started by the 43rd day after enrollment will be excluded from the analyses below.

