A patient enrolled without histological confirmation (see [Section 3.2.2.b](#)) will be considered evaluable for all study analyses unless the tumor tissue obtained in a future surgical procedure is not consistent with hepatoblastoma or reveals another pathological diagnosis. If histological confirmation is not confirmed in the future for these patients by a biopsy or surgical resection, they will be considered off study.

The statistical analysis will include an assessment of the influence of the exclusion of cases for whom there is a discrepancy in diagnosis between institutional and central review, or for whom there is an atypical histological presentation. The influence will be assessed by comparing the EFS and survival, as estimated by the method of Kaplan and Meier with and without such cases. This will provide an *ad hoc* assessment of the effect of such cases on outcome characterization. Formal statistical quantification of such effects will not be straightforward.

Surgical resection followed by observation was first tested on COG trial P9645 and has been demonstrated to be a successful approach for patients with stage I PFH. These patients will be enrolled on the trial, since

it will be necessary to submit all Stage I and II patients to mandatory central review to determine the appropriate analytic strategy. The results of this review will be returned for information to the relevant institutional investigator. Individuals considered Stage I PFH and treated with surgery only will be considered for the analysis described in the paragraph below. Individuals considered Stage I non-PFH, non-SCU, Stage II, non-SCU patients and treated with the chemotherapy for such patients will be considered in the analysis described in "[Hypothesis 1.1](#)" below.

[figure not shown]

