Nine (9) stage I PFH patients will be required for AHEP0731. We may enroll up to 12 patients to account for patients who are determined later to be ineligible. These patients will be followed closely for disease and life status. The outcome of these patients will be summarized through survival and EFS curves estimated by the method of Kaplan and Meier. If 2 or more analytic events are observed, the strategy of surgery without any further therapy will identify enrollment to this strategy for possible termination because of insufficient disease control. If this strategy is associated with a long-term event-free survival of 65%, the probability of accepting it is 0.12. If this strategy is associated with a long-term event-free survival of 93%, the probability of accepting it is 0.89.

Toxicity will be reported using CTCAE criteria (version 4). All Grade 3 or 4 or greater non-hematological toxicities as well as any toxicity that requires submission of an CTEP-AERS report as outlined in protocol [section 11.3](#), Table B, will be reported while the patient is on protocol therapy. The frequency of each toxicity type will be quantified as the percent of reporting periods on which the toxicity of the relevant grade is reported. All reporting periods where the patient receives at least one dose of each of the agents in the therapeutic plan for that individual will be included in the denominator for the rate calculation.

Follow-up data will be obtained on all patients considered eligible for the protocol. As part of the study design, slides sufficient to confirm the histological subtype of hepatoblastoma (PFH v. SCU v. neither PFH nor SCU) of all Stage I patients will be submitted to mandatory central review according to the time lines described above. Patients for whom the central review supports the therapeutic approach of the institutional investigator will constitute the analytic subgroup for each of the analyses planned for Stage I patients. The results of this review will be returned for information to the relevant institutional investigator as soon as the assessment becomes available in the COG data system.

Hypothesis 1.1: (Stage I, non-PFH, non- SCU, Stage II, non-SCU [Stratum 2]): Expected Annual Accrual: 9.2 patients per year. Total: 51 patients. We may enroll up to 60 patients to account for patients who are determined later to be ineligible.

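### Section 8.2(c) ends follow-up at entry to another COG treatment study, so survival is censored soon after relapse and the Kaplan-Meier survival summaries lean upward

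*Combined protocol and SAP*

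**What the plan says.** Four provisions act together.

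- **How long follow-up lasts.** Section 8.1: "Patients who are off protocol therapy are to be followed until they meet the criteria for Off Study". Progressive disease alone takes a patient off protocol therapy, not off study.
- **What ends it.** Section 8.2 lists death, loss to follow-up, withdrawal of consent for further data, the tenth anniversary of enrolment and failure to confirm the diagnosis. Item (c) is "Patient enrollment onto another COG study with tumor therapeutic intent (eg, at recurrence".
- **How survival is measured.** Section 9.2: "Survival will be the time from enrollment until death from any cause or last follow-up, whichever comes first".
- **How it is estimated.** For stratum 1, Section 9.2 says: "The outcome of these patients will be summarized through survival and EFS curves estimated by the method of Kaplan and Meier". For cases where institutional and central diagnoses differ, or the histology is atypical, it says: "The influence will be assessed by comparing the EFS and survival, as estimated by the method of Kaplan and Meier".

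Section 9.2 also says: "Follow-up data will be obtained on all patients considered eligible for the protocol". It adds that stratum 1 patients will be followed closely for disease and life status. Neither sentence says that this continues once an off-study criterion has been met.

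**The concern.** Kaplan-Meier assumes that patients censored at a given time go on to die at the same rate as those still at risk at that time. A patient who leaves under 8.2(c) at recurrence does not meet that assumption. The reason for censoring is that the trial strategy has failed. The patients who remain at risk are mostly event-free, with a much lower death rate. Deaths after relapse drop out of the estimate and the curve sits too high.

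What is at stake is how survival is read beside EFS. Section 2.3.2 sets an EFS of 84% beside a survival of 96% for low-risk patients. Section 2.3.3 suggests that the better survival on P9645 may reflect salvage with doxorubicin. If readers compare AHEP0731 with those studies in the same way, the gap between EFS and survival will partly be produced by the follow-up rule.

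**Working it through.** The plan states no survival estimate, power or sample size, so there is no figure of its own to reproduce. The check has two parts.

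**1. Direction, from the text.** Relapse occurs and the EFS event is counted, since "progression of existing disease or occurrence of disease at new sites" is an analytic event. Protocol therapy stops (8.1a) and follow-up continues. The patient enters another COG treatment study and goes off study (8.2c), so last follow-up falls shortly after relapse. If alive then, the patient is censored for survival at that date. Nothing in Sections 8 or 9.2 provides for life status after 8.2(c), for linkage to the later study, or for an analysis that allows for informative censoring.

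**2. Size, from an illness-death model.** Inputs from the documents:

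- low risk: EFS 84%, survival 96% (Section 2.3.2, given as 5-year; Table 1 marks the same pair as 4-year)
- Stage III: 5-year EFS 64%; survival about 70%, reported for localized disease (Section 2.3.3, INT-0098)
- Stage IV: 5-year EFS 25%; survival about 35%, reported for metastatic disease (same place)

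Assumptions:

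- the 70% and 35% are 5-year values
- first events occur at a constant rate over the first W = 1, 2 or 3 years
- a share q = 0 or 10% of first events are deaths
- the death hazard μ after relapse is constant
- a share f of relapsed patients enter another COG study L = 1 or 3 months after relapse, with the same μ as other relapsed patients

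Formulas:

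- Event hazard: λ = −ln(EFS)/W up to W, then 0.
- Event-free at t: A(t) = exp(−λ·min(t, W)).
- Relapsed, alive and still followed: B_f(t) = ∫ (1−q) λ A(s) exp(−μ(t−s)) [1 − f·1(t−s > L)] ds, for s from 0 to min(t, W).
- μ is solved so that A(5) + B_0(5) equals the quoted survival.
- Death hazard that Kaplan-Meier sees: h_f(t) = [qλA(t) + μB_f(t)] / [A(t) + B_f(t)], with the λ term only up to W.
- Large-sample Kaplan-Meier value at 5 years: exp(−∫ h_f(t) dt), from 0 to 5.

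Worked case, Stage IV with W = 2, q = 0 and L = 1 month: λ = −ln(0.25)/2 = 0.693 per year, and μ solves to 0.49 per year. With f = 0 the value is 0.35, the true survival. With f = 10%, 25% and 50% it is 0.37, 0.41 and 0.49. A simulation of 400,000 patients for this case gave 0.405 at 25% and 0.492 at 50%, against a simulated true value of 0.348.

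Ranges over all W, q and L:

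| Setting | True 5-year survival | f = 10% | f = 25% | f = 50% |
|---|---|---|---|---|
| Low risk | 96% | 96.2-96.3% | 96.5-96.9% | 97.0-97.8% |
| Stage III | 70% | 72% | 74-75% | 79-82% |
| Stage IV | 35% | 37% | 39-41% | 46-50% |

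Subtracting the true value gives overstatements, in points, of about 0.2-0.3, 0.5-0.9 and 1-2 in low risk; 2, 4-5 and 9-12 in Stage III; and 2, 4-6 and 11-15 in Stage IV.

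**The case against.** The case on the other side is substantial, and much of it stands.

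- **Survival has a small role.** No aim in Sections 1.2 or 1.3 is survival. Strata 1 and 2 are judged on analytic events, stratum 3 on on-therapy deaths, stratum 4 on responders, and referral on a count. Kaplan-Meier survival is specified only for stratum 1 (9 patients, up to 12 enrolled) and for the ad hoc comparison with and without discrepant cases, where 8.2(c) acts on both sides. This stands. The Stage III and IV figures show what the rule would do to survival curves for which 9.2 plans no stratum-specific analysis.
- **The share joining may be low.** Section 2.3.4 says most pediatric phase 1 and 2 studies include fewer than two patients with liver tumors, and the relapse trial of irinotecan that it mentions is a SIOPEL trial, which would not trigger 8.2(c). Section 2.3.4.2 says the cited phase I temsirolimus study entered no hepatoblastoma patients. This gives no value for f but points toward the lower end.
- **Entrants may be fitter than other relapsed patients.** The bias would then be smaller, but it stays upward while their death rate exceeds that of the patients still at risk.
- **Censoring at the off-study date is inferred.** Section 9.2 censors at last follow-up, and Section 3.1.1 says the COG patient ID identifies the patient in all future dealings with COG, so later status might be used. The plan does not forbid this, but it does not provide for it, and 8.1 ends follow-up at the off-study criteria.

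A reader might also infer that EFS is biased. The documents do not support that for relapsed patients, because the relapse is counted before 8.2(c) acts. A patient taken off protocol therapy without an event could join another COG study and be censored for EFS, but nothing shows how often. Part of that route is closed, since Stage III disease still present after four cycles and any attempted surgery is already a treatment-failure event.

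**Conclusion.** The concern holds as a point about a secondary summary. Read as written, 8.2(c) with the survival definition in 9.2 censors relapsed patients informatively, and the bias in Kaplan-Meier survival is upward. That direction rests on the text and on relapsed patients who join another study having a higher death rate than those still at risk.

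The size is illustrative. It rests on the assumed share f, constant hazards, and a 5-year reading of approximate survival figures from earlier trials. At low-risk rates it is under 1 point for f up to 25%. At Stage III/IV rates it is about 2 points at 10% and grows quickly with f.

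A reader might infer that the trial's reported survival will be materially too favourable, or that its main conclusions are at risk. Neither follows. The share joining is unknown, and no primary aim or decision rule depends on survival.

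**What to change.** - **Section 8.2(c):** amend so that entry to another COG therapeutic study ends treatment-related data submission only. Date of last contact and life status continue until death, the tenth anniversary of enrolment or withdrawal of consent, taken from the later study's COG record where available and where consent allows.
- **Section 9.2:** state that survival is not censored at entry to another study, and report how many patients could not be followed past that point.

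If the group already carries life status across its studies, a sentence in 9.2 saying so, with that count, is enough.

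The cost is a short change in each section and continued collection of life status, for patients whom the same group is following elsewhere. Two limits apply. The study closed on July 20, 2018, so status may not be recoverable for some patients already off study. Whether existing consent covers the added collection cannot be checked here, because the consent pages were removed from the copy reviewed.

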## 9.0 STATISTICAL CONSIDERATIONS

### 9.1 Patient Accrual and Expected Duration of Trial

Patients will be enrolled for five (5) years and analyses to address the primary study aims will be conducted with one more year of follow-up. The projected annual enrollment rates for each of the categories of patients are:

Stratum	Patient Category	Estimated Annual Accrual
1	Stage I PFH with initial AFP $\geq$ 100 ng/mL or AFP not obtained prior to initial resection	3 patients per year
2	Stage I, non-PFH, non-SCU, Stage II, non-SCU	9.2 patients per year
3	Intermediate risk	41.6 patients per year
4	Stage IV or patients with AFP <100 ng/mL at diagnosis	16 patients per year

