If 7 or more analytic events are observed the strategy of surgery with reduced chemotherapy will identify enrollment to this strategy for possible termination because of insufficient disease control. If this strategy is associated with a long-term event-free survival of 78%, it will be rejected with probability 0.90. If this strategy is associated with a long-term event-free survival of 89%, it will be accepted with probability 0.81. The graph below describes the probability of accepting the strategy as a function of its long-term EFS:

Hypothesis 1.2 (Intermediate-risk patients [Stratum 3]): As of Amendment #3B enrollment to stratum 3 is terminated because sufficient patients have been enrolled to address the hypothesis. The total enrollment to stratum 3 was 105 patients.

*Feasibility of Delivery of C5VD*: The primary measure of feasibility will be rate of death as a first analytic event. All patients who receive at least one dose of the C5VD regimen will be considered evaluable for this endpoint. Any patient who dies on protocol therapy or within 30 days of the termination of protocol therapy of a cause considered possibly, probably or likely related to systemic chemotherapy will be considered to have experienced an on-protocol-therapy death. If five or fewer of the 99 patients experience on-protocol-therapy death, the regimen will be considered feasible for further development. If the regimen is associated with a death-event rate of 3%, that observed for patients who were assigned to chemotherapy on P9645, the regimen will be considered feasible with probability 0.92. If the regimen is associated with a death-event rate of 10%, the regimen will be considered not feasible with probability 0.94. If the sixth on-protocol-therapy death is reported, study enrollment will be suspended. In addition to this, at each report to the DSMC the estimated on-protocol-therapy death rate and its 95% confidence interval will be reported to the phase III DSMC as the cumulative incidence of on-treatment death and the 95% confidence intervals at four and six months.

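### Stratum 2's stated enrolment period, accrual rate and size do not fit together: 9.2 patients per year for five years projects 46, not 51

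*Combined protocol and SAP*

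**What the plan says.** The enrolment period appears twice. Section 9.1 has: "Patients will be enrolled for five (5) years and analyses to address the primary study aims will be conducted with one more year of follow-up". Section 9.2, in its Statistical Considerations text, repeats it: "Patients will be enrolled to the study for Five years and followed for an additional year".

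The Stratum 2 paragraph (Hypothesis 1.1 in Section 9.2) gives the rate and the size: "Expected Annual Accrual: 9.2 patients per year. Total: 51 patients". It then sets a ceiling: "We may enroll up to 60 patients to account for patients who are determined later to be ineligible". The table in Section 9.1 shows the same 9.2 per year.

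The decision rule is a fixed event count: "If 7 or more analytic events are observed the strategy of surgery with reduced chemotherapy will identify enrollment to this strategy for possible termination". Its stated properties are that, with a "long-term event-free survival of 78%, it will be rejected with probability 0.90", and with a "long-term event-free survival of 89%, it will be accepted with probability 0.81".

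**The concern.** Period, rate and size are three statements of one quantity, and any two of them fix the third. Here they disagree, and the follow-up year adds no patients. Stratum 2 carries primary aim 1.2.1, the EFS estimate after chemotherapy is cut from four cycles to two, and Section 2.3.2 relies on strict monitoring and stopping rules to make that reduction safe.

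The plan does not say which figure yields if accrual runs as projected. If the size yields, a fixed event count is applied to fewer patients than the 51 planned, and a strategy with poor EFS becomes easier to accept. If the period yields, the rule keeps its planned size but the stated duration and analysis date are too early.

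**Working it through.** **Inputs.** Enrolment 5 years, then 1 year of follow-up (Sections 9.1 and 9.2). Stratum 2 rate 9.2 per year, size 51, ceiling 60, flag at 7 or more events, rejection 0.90 at 78% EFS, acceptance 0.81 at 89% EFS (Section 9.2). Study-wide ineligible and inevaluable rate 10% (Section 9.3). Study activated 14 September 2009 and closed 20 July 2018 (dates printed with the summary of changes).

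**1. The plan's own probabilities.** Exact binomial with n = 51, event probability 0.22 (78% EFS) or 0.11 (89% EFS), taking each patient's long-term event status as known:

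- Flag at 7 or more, as written: P(X ≥ 7 | 0.22) = 0.952; P(X ≤ 6 | 0.11) = 0.673. These do not reproduce 0.90 and 0.81.
- Flag at 8 or more: P(X ≥ 8 | 0.22) = 0.900; P(X ≤ 7 | 0.11) = 0.806. These reproduce both.

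So the stated probabilities belong to 51 patients with a cut-off of 8, while the text says 7. This is a separate discrepancy, but it matters for any restatement.

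**2. Accrual.**

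- Projected in five years: 9.2 × 5 = 46. Shortfall 51 − 46 = 5 patients (5/51 = 9.8%).
- Time to 51: 51/9.2 = 5.54 years.
- Time to 51 eligible if 10% are lost: 51/0.9 = 56.7 enrolled; 56.7/9.2 = 6.16 years.
- Time to the ceiling of 60: 60/9.2 = 6.52 years.

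With the one-year follow-up, the analysis falls at year 6 as written, but at about year 6.5 for 51 enrolled and 7.5 for 60.

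**3. The other strata at their stated rates.** Stratum 1: 12/3 = 4.0 years. Stratum 3: 105/41.6 = 2.5 years. Stratum 4: 43/16 = 2.7 years, or (43 + 30)/16 = 4.6 years if the earlier window cohort of 30 (Section 2.3.4) is added. All fit within five years. Only Stratum 2 does not.

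**4. If enrolment were held to five years.** Eligible patients out of 46 enrolled:

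- 46, if 9.2 per year already excludes ineligible patients;
- 46 × 0.90 = 41.4, if the study-wide 10% applies;
- 46 × 51/60 = 39.1, using Stratum 2's own allowance (9/60 = 15%).

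| n | Reject 78% EFS, flag at ≥ 7 | Accept 89% EFS, flag at ≥ 7 | Reject 78% EFS, flag at ≥ 8 | Accept 89% EFS, flag at ≥ 8 |
|---|---|---|---|---|
| 51 | 0.952 | 0.673 | 0.900 | 0.806 |
| 46 | 0.906 | 0.762 | 0.824 | 0.873 |
| 41 | 0.828 | 0.841 | 0.708 | 0.925 |
| 39 | 0.785 | 0.869 | 0.650 | 0.941 |

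**5. The printed dates.** Activation to closure is about 8.85 years. That span would deliver 51 patients at 51/8.85 = 5.8 per year, or 60 at 6.8 per year.

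**The case against.** A reader might infer that the rule would be applied to about 46 enrolled, or about 41 eligible, patients. The case against that reading is strong, and most of it stands.

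- No text closes Stratum 2 short of its number. Section 9.2 fixes a total of 51 with room to 60, and Section 9.1 calls its duration expected and its rates projected.
- The other strata are governed by counts. Section 2.3.3 says Stratum 3 was suspended when its required number had been enrolled, about 2.5 years after activation. Stratum 1 is capped at 12, although five years at 3 per year would give 15. Stratum 4 is set at 43, although five years at 16 per year would give 80.
- The study stayed open for about 8.85 years, so enrolment to the study as a whole seems not to have stopped at five. Stratum 2's own closing date and accrual are not given, so its achieved size cannot be checked either way.
- The figure of 41 needs 9.2 to be a gross rate and the study-wide 10% to apply to this stratum. The plan states neither.
- At 46 patients with the written cut-off, rejection at 78% EFS is 0.906, which still meets the stated 0.90, and acceptance at 89% EFS rises from 0.673 to 0.762. The stated protection is lost only with a smaller eligible number or with a cut-off of 8.
- A projected rate does not make 51 impossible. If five-year accrual were Poisson with mean 46 (an assumption, not in the plan), the chance of 51 or more would be about 0.25.

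What the objection does not remove is the mismatch itself. A plan should be consistent at its own projected rate, and this one is not. The version dated 11/07/18 also still states five years beside dates that span nearly nine.

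**Conclusion.** Wrong as written; minor. At the stated rate, five years projects 46 patients against a size of 51, and the period is about 0.5 year short for 51 enrolled and 1.5 years short for 60. Since the strata are sized by count, the more natural reading is that 51 governs and that the duration and the aim 1.2.1 analysis date are understated by that much.

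The documents do not support the stronger conclusion that the rule will be, or was, run on about 46 or 41 patients. That is a conditional result: it needs enrolment to be held to five years, and below 46 it also needs an assumed ineligible rate. Under those conditions and the written cut-off, the chance of rejecting a 78% EFS falls from 0.952 to between 0.906 (n = 46) and 0.785 (n = 39). These probabilities assume independent patients whose long-term event status is known.

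**What to change.** In Sections 9.1 and 9.2, choose which figure governs Stratum 2 and make the others follow.

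- **If 51 governs:** state that Stratum 2 enrols until 51 eligible patients are reached, project 5.5 to 6.5 years at 9.2 per year, and tie the aim 1.2.1 analysis to one year after that enrolment ends.
- **If five years governs:** restate the size as about 46 enrolled, say whether 9.2 per year is before or after ineligible patients, give the eligible number that follows, and restate the rule's probabilities for that number.

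In either case, first reconcile the written cut-off of 7 or more with the stated 0.90 and 0.81, which match 8 or more at 51 patients. Otherwise any restated probabilities rest on an unclear rule.

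The cost is wording, plus either a longer stated duration or a smaller stated size. As this version post-dates closure of the study, the practical gain is a consistent record and a clear statement of when, and on how many patients, the Stratum 2 rule is to be read.
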